Creative Arts Therapy (CAT) in the Center for Cancer and Blood Disorders

[name]

Associate Professor, Pediatrics

University of Colorado

Children's Hospital Colorado

NCT04208243

COMIRB Protocol

PROTOCOL #: 10-1028

**COLORADO MULTIPLE INSTITUTIONAL REVIEW BOARD
[name] [contact]
[contact]**

Project Title: Creative Arts Therapy (CAT) in the Center for Cancer and Blood Disorders

Principal Investigator: [name], MSN, CPNP

Co-Investigators: [name], CPNP

Version Date: 5/10/2019

I. Hypotheses and Specific Aims

The purpose of the study is to evaluate the effectiveness of Creative Arts Therapy (CAT) on pediatric patients undergoing chemotherapy in the Infusion Center at Children's Hospital Colorado Center for Cancer and Blood Disorders. Findings from a previous pilot study support the hypothesis that CAT may improve quality of life (QOL), resiliency, physical posture, and emotional response to pain of pediatric oncology patients undergoing chemotherapy.

Specific aims include:

- a. Does CAT improve the child's reported QOL?
- b. Is the child's resiliency enhanced by CAT?
- c. Does CAT influence the physical posture of the child?
- d. Does CAT impact the child's emotional response to pain?
- e. Are patients, families, and staff satisfied with the CAT program?

II. Background and Significance

Although survival rates of children with cancer are improving, their QOL is known to be poorer than their healthy peers. As survival rates of pediatric cancer now approach 85%, the need for quality psychosocial care including creative arts has increased (Askins & Moore, 2008). Oncology patients are known to have significant morbidity during treatment as a result of the surgery, radiation and chemotherapy, but little is published on the day to day effects of treatment on the quality of life of pediatric oncology patients (Banks, 2008). Tremolada et al looked at parental perception of QOL in newly diagnosed children with leukemia and found that increasing the knowledge of QOL may improve communication and psychosocial care during initial treatment for leukemia (2010). In addition, quality of life among adolescents with cancer may be worse during treatment than for those not currently on therapy (Ward-Smith et al., 2007). Another study has shown that interventions to promote happiness may be a good predictor of QOL in adolescent cancer survivors (Bitsko et al., 2008).

It has been acknowledged that even the act of coming to the clinic weekly for chemotherapy infusions impacts on the patient's life. In addition, vincristine, a commonly used chemotherapy, is also well-known to cause significant morbidity (leg pain, numbness, tingling, and constipation) requiring dose-limiting regimens. Steroids are another common medication

with toxicities affecting QOL. Toxicities of steroids include weakness, sleep and mood disturbance, and pain with dose reduction (Sanford et al., 2008; Hinds et al., 2007).

Resilience is a subset of QOL that has been studied in pediatric chronic illness including cancer (Haase et al., 2004). Resilience has been defined as a characteristic that moderates stress and the ability to cope with change or misfortune (Wagnild & Young, 1993). Resilient individuals have positive outcomes in spite of adversity (Rew & Horner, 2003). Therefore nurses who understand resilience can promote those characteristics during times of illness or stress (Ahern et al., 2006). There is a paucity of literature directly studying resilience in pediatric oncology patients and further work is warranted.

Emotional response to pain is another subset of QOL that has been measured in this population. It is well known that pediatric oncology patients experience pain (Lervat, 2009). Experts recommend rigorous research using established measures to evaluate childrens' response to pain (McGrath et al., 2008). The Faces scale has been studied with children as young as 5 years to evaluate their emotional response to pain compared with their parents' perceptions (Breau et al., 2001). Pilot data on emotional response on the Faces scale has been shown to improve after group CAT (Madden et al., 2010).

Physical functioning and muscle strength are aspects of QOL that have been shown to be worse than healthy peers in children with cancer (Hartman et al., 2008). This aspect may also be affected by the central venous access lines placed in almost all pediatric cancer patients. Long-term central venous access is critical in pediatric cancer patients and the evolution of these devices has improved QOL in terms of pain and distress of venipuncture (Spagrud, 2008). The literature is rich with discussion of complications and risk of infection, but little is published about the effects on body image and QOL (Albanese, 1993; Nam, 2010). Anecdotally, patients have improved body awareness and posture (less kyphosis) after CAT. In addition, it has been postulated that increased kyphosis may correspond with psychosocial factors including anxiety, depression, and insecurity. Body awareness is a type of physical functioning that may be measured by kyphosis. Measuring posture with an inclinometer has been shown to be reliable, but further work is needed to establish validity (Lewis & Valentine, 2010). Piloting this tool may establish a way to physically measure an individual's sense of self by the way that he or she stands.

The use of complementary and alternative medicine (CAM) is one intervention that has been shown to improve QOL in this population. Current trends show increasing popularity of the use of CAM in even among children with cancer. Martel et al (2005) looked at prevalence of use of CAM in children. In their survey, almost 50% of the children used at least one type of CAM. Specifically to cancer, in 2009, Post-White et al used a survey of 281 patients to show that CAM was used in 59% of pediatric cancer patients versus 36% of general pediatric patients. The authors confirmed that children with cancer and other chronic illnesses use more CAM therapies than children seen in primary care clinics. Roth et al (2009) examined pediatric oncologists' perceptions of CAM and found that although they place importance in CAM, they lack time and knowledge to ask about patients' use of CAM. These authors recommend CAM research in pediatric oncology on modalities that could improve QOL.

CAT is a subset of CAM that may improve QOL. CAT is a broad term encompassing the modalities of dance/movement, music, art. Bringing creativity into health care is a current trend in oncology nursing and throughout the medical professions (Garland et al., 2007; Lane, 2006; Petterson, 2001; Strickland, 2008). There is a growing body of literature establishing the use

of CAT, but the studies use non-standardized tools, small sample sizes, adult populations, and non-rigorous designs. Much of the work on CAT in cancer patients studies adult populations using qualitative measures (Forzoni et al, 2010; Jones et al., 2009; Visser, et al, 2008; Bar-Sela, et al., 2007; Nainis et al., 2006). Other work looked at the family caregivers of patients with cancer and showed significantly reduced stress, anxiety, and increased positive emotions after a creative arts intervention (Walsh et al., 2004). Randomized controlled studies are in the literature and have shown improvement in QOL, but only for the population of women with breast cancer (Oster et al, 2006; Monti et al, 2006; Svensk et al, 2009; Thyme et al, 2009). Music was shown to decrease heart rate in children with leukemia, but the therapeutic aspects were not studied (Kemper et al., 2008). The literature is rich with other examples of types of music, art, movement therapies that may improve QOL in adult and pediatric oncology patients, but there are few rigorous studies to document the importance of CAT during the cancer treatment (Sencer et al, 2007; Dibell-Hope, 2000; O'Callaghan et al, 2007; Robb et al, 2003; Barrera, 2002; Hilliard, 2006).

Therefore, a pilot study of CAT on the QOL of pediatric brain tumor patients used a mixed-model approach with a randomized, controlled phase comparing CAT to a control. Pre- and post- measurements using the PedsQL showed statistically significant improvement on Parent report of child's hurt (problems with having a lot of pain), $p=0.03$ and Parent report of child's nausea (becoming nauseated while thinking about medical treatment), $p=0.0061$. The second non-randomized phase pre- and post- tested any child in group session of CAT. The subjects showed improved mood with statistical significance on the Faces Scale ($p < 0.01$), and patients were more excited ($p < 0.05$), happier ($p < 0.02$), and less nervous ($p < 0.02$) on the Emotional Responses Checklist (Madden et al, 2010).

Rationale

The pilot study was limited by the small sample size; therefore we propose a study with a larger sample size and broader inclusion criteria. We would also like to explore outcomes of resilience and body awareness measured by physical posture based on our observations during the pilot study.

Significance

Nurses have been shown to provide valuable information on QOL for this population (Klaassen et al, 2010). In addition, the pediatric oncology nurse is in a key position to incorporate the art and science of nursing to improve psychosocial treatment outcomes (Cantrell, 2007). Therefore this nursing research study will provide valuable insight to contribute to the body of knowledge of CAM for pediatric oncology patients. The use of CAM for pediatric oncology patients may improve QOL, resiliency, emotional response, and body awareness.

III. Preliminary Studies/Progress Report

See above regarding the previous pilot study. Small sample size limited the statistical significance.

IV. Research Methods

A. Outcome Measure(s)

1. Peds QL—Cancer module

The PedsQL 4.0 Cancer Module is evolved from the PedsQL 4.0 Generic Core Scale (Varni, 1998). The system employs a Parent-Proxy Report for ages 2-18 years and a companion Child Self-Report for children aged five years and older. Validity and reliability testing for both the Core Scale and Cancer Module has been extensive.

Reliability, assessed by internal consistency, yielded coefficient alphas ranging from .80-.90 across total and individual scales and are, thus, appropriate for the group comparisons planned in this study. The Cancer Module is a 27-item instrument that assesses eight subscales (Pain and hurt, nausea, procedural anxiety, treatment anxiety, worry, cognitive problems, perceived physical appearance, and communication). It is easily completed by parents in less than 10 minutes and reverse-scored and linearly-transformed in five minutes or less. Validity for both the Core Scale and the Cancer Module was established by expert panel review; similarly, construct validity for both measures was performed by comparing the responses of children with cancer across both measures to a group of healthy matched controls. In all cases, the Peds QL 4.0 Cancer Module was able to distinguish the responses of children with cancer from those of healthy children at a statistically significant level.

The instruments have been successfully employed in several small studies of children with cancer (Bhat, 2005; Meeske et al, 2004). The PedsQL has been shown to be the most responsive to change when compared with other measures of QOL used with children undergoing chemotherapy (Banks et al, 2008; Klaassen et al, 2010).

2. *The Resilience Scale (RS)*

The RS-14 is a 14-item scale using a 7-point rating (1-7). The construct of resilience is measured by two factors: personal competence and acceptance of self and life. Wagnild and Young have completed psychometric testing that established internal consistency reliability and concurrent validity (Wagnild & Young, 1993). Many studies have validated that the scale may be used with samples of any age or ethnic background (Ahern et al, 2006), but it is written at a 6th grade level. The authors who developed the tool are currently using it in adolescents (personal communication, 5/25/10). Given that it is expected that half the population of this study will be teenagers, this tool will be used with subjects ages 12 and over to obtain initial data on CAT's effect on resilience.

3. *Faces Scale*

The Faces Scale has been used for evaluating emotional responses to pain on children 3-17 years old. It is a one page form with nine faces in order of happy to upset. Numerical values are given to each face as determined by childrens' perspectives for an affective value by asking 200 children to directly scale the feelings depicted by the faces. Consistent rating was measured by children over 5 years regardless of age, gender, or health status (McGrath, 1990). The scale is a facial affective scale and has been integrated as a routine measure for management of acute, recurrent, and chronic pain (McGrath, 1990; McGrath et al., 1996). For children less than 3 years old, parents will be asked to complete the Faces Scale. Although this scale has been used for emotional response to pain, it is felt to be an appropriate measure for the emotional response to the discomfort and anxiety in the infusion room.

4. *Postural Measurement*

Thoracic kyphosis will be measured using two gravity dependent inclinometers (Isomed Inc.). Spinal processes will be determined by palpation by a registered nurse or pediatric nurse practitioner. The feet of the inclinometers will be placed over the spinal processes thought to be at T1, T2 and T12, L1. The measurements will be taken in relaxed standing and measured 3 times in succession. Clinical assessment of the thoracic kyphosis angle is considered essential in postural examination, but can be time

consuming when measured radiographically (Lewis, 2010). Lewis and Valentine studied intra-rater reliability in subjects with and without symptoms and found measurements of less than 1.7 degrees should be considered measurement error. The test-re-test reliability established excellent intra-rater reliability. Although validity of this measure is less studied, the measurement is thought to provide guidance of how much change of the kyphoscoliosis angle is a real consequence of intervention over time (Lewis, 2010).

5. Patient/Family Surveys

A brief ten minute written survey will be administered to subjects to ascertain level of satisfaction with the program.

B. Description of Population to be Enrolled: Study Design and Research Methods

1. Population

The Center for Cancer and Blood Disorders (CCBD) at Children's Hospital Colorado sees approximately 240 new Oncology patients each year. Approximately 45% of these patients receive vincristine, a chemotherapy agent that is known to affect physical functioning. In addition, about 25% of these patients receive steroids, another medication known to affect physical functioning and quality of life. About half of the new patients each year are anticipated to fit the inclusion criteria. Therefore, we expect approximately 100 eligible subjects per year, with a 50% attrition rate, for a total sample size of 100 subjects over a two year period.

Enrollment for this study was reached in 2019. At this time, an additional 10 patients will be allowed to enroll on study to help supplement the data.

2. Eligibility Criteria

Inclusion

- Center for Cancer and Blood Disorders (CCBD) patient with Oncology or Neuro-oncology diagnosis
- No more than 2 previous sessions of CAT as an outpatient in the CCBD
- English speaking
- Receiving outpatient chemotherapy, biotherapy, or transfusions in the infusion center approximately weekly for at least 3 months.
- Ages 3 to 18 years

Exclusion

- Hematology or other patients in the infusion center
- Patients who have previously received more than 2 sessions of CAT in the infusion center
- Non-English speaking patients

3. Study Design

A repeated measures design will be used with each patient serving as his/her own control.

Any Oncology patient in the CCBD who has not previously received more than two sessions of CAT in the outpatient unit and who will be receiving approximately weekly infusions of at least one hour in the infusion center will be identified by a research assistant. The study will be explained to the patient/family and informed consent will

be obtained by the principal investigator or the research assistant. A demographic form will be completed including the information of diagnosis, age, treatment, educational level of parents, zip code, prior experience with art, music, movement.

The intervention will consist of approximately weekly CAT in the infusion center during cancer therapy. The interventionist is a Master's prepared, licensed dance/movement therapist who is experienced in music and art therapies as well. The CAT includes dance/movement such as playing with a parachute, simple yoga breathing and postures, and work with physioballs. The music includes singing, listening to music, and playing instruments. The art consists of drawing, finger painting, working with clay. The CAT may occur in individual sessions in private infusion rooms, or in groups in the middle of the infusion center. The CAT is not only a distraction, but also a therapeutic process addressing the stressors of cancer and its treatment. The "dose" of CAT will be recorded (number and type of sessions) and will be factored into the analysis.

The subjects and/or parents will be tested with all instruments before the intervention, and approximately every 30 days for no less than 3 months and a maximum participation of 6 months. Treatment time points will be at least 30 days apart. Because some subjects are not scheduled to come into the clinic every 30 days for SOC appointments, they are unable to complete 3 sessions of CAT in a 3 month time period. For those subjects who are scheduled to come into clinic every 1-2 months for SOC appointments, study participation may take up to 6 months. This 6 month time period would allow for the completion of 4 different time points of CAT.

The testing will take place in an exam room after vital signs have been completed upon intake to the clinic. The trained research assistant, trained RN, or PI will administer the questionnaires. The PedsQL includes a subject report (ages 5 and over) and a parent report. The Resilience Scale is a self-report and will be used for ages 12 and over. The Faces Scale will use parent report for ages less than 5 and self-report for ages 5 and over. In order to confirm consistency, the posture measure will be completed by the PI (nurse practitioner) or registered nurse on the study after training with the manual included with the inclinometer tool.

Off Study Criteria

1. Subject discontinues CAT
2. Unable to complete 4 time points in 6 months

C. Description, Risks and Justification of Procedures and Data Collection Tools

The anticipated risks include psychological distress incurred by completing the outcome measure questionnaires as well as the therapeutic process. This risk will be minimized by the presence of the Master's prepared, experienced dance/movement therapist. The patients' social workers through the clinic will be available during the intervention as well.

D. Potential Scientific Problems

Based on the pilot data, the anticipated scientific problem is slow accrual due to unforeseen events during the traumatic time of a new diagnosis in pediatric oncology. We are unable to randomize because CAT is standard of care for any patient in the infusion center and therefore we feel it is unethical to deny CAT to a control arm. Therefore, we will compare the subjects to themselves over time to look at longitudinal changes of CAT.

E. Data Analysis Plan

The primary outcome is Peds QL at approximately 3 months; secondary outcomes will be the Resilience Scale, Faces Scale, and postural measurement at approximately 3 months. A repeated measures analysis of variance will be used to analyze the primary and secondary outcomes. We will also use the repeated measures analysis of covariance with the addition of covariates, depending on their statistical significance, such as gender, age, cancer diagnosis, and previous exposure to arts/music/dance. All of the analysis will be adjusted for baseline measures.

We expect to recruit 100 patients, we also expect patients will be equally distributed in the following 3 categories: receiving low (0-3), intermediate (4-6) and high (7+) CAT sessions due to the nature of each patient's random visits. Power analysis was done based on pair-wise T-Test with these assumptions for simplicity. With 33 patients in each group, assuming 80% power and 0.017 significance level of alpha after Bonferroni ad justification of multiple comparisons, we will observe a minimum effect size of 0.813. This is to say that 80% of the Peds QL scores in the lower session CAT group will be below the average of scores in the higher session CAT group. Thus, what we would expect to see in the positive dose-response relationship.

We will also conduct subgroup analysis by age group if the sample size is large enough since Peds QL is designed by age group.

F. Summarize Knowledge to be Gained

Integrative and holistic therapies are being used throughout healthcare. We know that families are using alternative therapies without rigorous evidence documenting their worth. We therefore strive to build a body of literature showing evidence that CAT helps children with cancer feel better.

G. Appendices

1. PedsQL
2. Resilience Scale
3. Faces Scale
4. Inclinator information
5. Patient/Family Survey

H. References:

- Bhat SR, et al. (2005) Profile of daily life in children with brain tumors: an assessment of health-related quality of life.[see comment]. *J Clin Oncol*, 23, 5493-5500.

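### The fourth assessment can fall anywhere from day 90 to day 180, but the 3-month PedsQL analysis has no visit window and no term for actual time, and CAT dose has no counting period

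*Combined protocol and SAP*

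**What the plan says.** Section IV.B.3 (Study Design) has all instruments given before the intervention and then "approximately every 30 days for no less than 3 months and a maximum participation of 6 months". It sets a minimum gap: "Treatment time points will be at least 30 days apart". It recognizes that some children do not attend every 30 days and extends the period for them: "For those subjects who are scheduled to come into clinic every 1-2 months for SOC appointments, study participation may take up to 6 months". It adds: "This 6 month time period would allow for the completion of 4 different time points of CAT". I read these time points as assessments, which fits a baseline plus three tests about 30 days apart. The off-study criteria remove a child only if four time points cannot be completed in 6 months.

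On the order of events within a visit: "The testing will take place in an exam room after vital signs have been completed upon intake to the clinic".

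Section IV.E (Data Analysis Plan) states: "The primary outcome is Peds QL at approximately 3 months". The method is: "A repeated measures analysis of variance will be used to analyze the primary and secondary outcomes". Covariance analysis and adjustment for baseline are also planned. The covariates named as examples do not include time since baseline.

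On dose, Section IV.B.3 says that the amount "of CAT will be recorded (number and type of sessions) and will be factored into the analysis". Section IV.E uses three session bands (0-3, 4-6, 7+) in its power calculation and expects a positive dose-response. Neither section gives the period over which sessions are counted.

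**The concern.** Repeated-measures ANOVA treats the nth assessment as the same occasion for every child. That is harmless when visits follow a common calendar. Here the calendar depends on how often a child attends, and the only limits are a 30-day minimum gap and a 6-month cap. Neither is a window around 3 months.

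Two results are at stake. First, the 3-month estimate of change becomes an average over different lengths of follow-up. With no randomized control, within-child change over time is the main evidence, so what counts as 3 months matters. Second, attendance also governs how many sessions a child can receive. If PedsQL changes with time on treatment, a difference in timing between dose groups can look like a dose effect or hide one. Baseline adjustment does not correct for unequal follow-up time. Without a counting period, sessions held after an outcome could also be used to explain it.

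**Working it through.** **The plan's own figure.** A two-sample t-test with 33 per group, two-sided alpha 0.017 and 80% power gives a detectable effect of 0.8129, which matches the stated 0.813. Power is not at issue here.

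**Inputs.** From Section IV.B.3: four assessments, a gap of at least 30 days, a 6-month cap, testing at intake. My assumptions: exact visit intervals of g days from day 0, one CAT session per visit, and the session following that day's testing. The documents do not state one session per visit. Day 180 is derived from three 60-day intervals; the protocol says 6 months.

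**Formulas.** The assessment gap is the smallest multiple of g that is at least 30 days, and the fourth assessment falls at three gaps. Sessions before day D = D/g, rounded up.

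| Visit interval (days) | Assessment days | Sessions before day 90 | Before day 180 | Before fourth assessment |
|---|---|---|---|---|
| 7 | 0, 35, 70, 105 | 13 | 26 | 15 |
| 14 | 0, 42, 84, 126 | 7 | 13 | 9 |
| 21 | 0, 42, 84, 126 | 5 | 9 | 6 |
| 30 | 0, 30, 60, 90 | 3 | 6 | 3 |
| 45 | 0, 45, 90, 135 | 2 | 4 | 3 |
| 60 | 0, 60, 120, 180 | 2 | 3 | 3 |

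**Timing.** The fourth occasion ranges from day 90 to day 180. It is not always the one nearest day 90: for 14-, 21- and 45-day attenders that is the third (day 84, 84 and 90). A 60-day attender has no assessment near day 90; days 60 and 120 are equally far from it.

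**Dose.** Counting to day 180 instead of day 90 moves a 21-day attender from 5 to 9 sessions (intermediate to high band), a 30-day attender from 3 to 6 and a 45-day attender from 2 to 4 (both low to intermediate). Counting to the fourth assessment gives 3 sessions to 30-, 45- and 60-day attenders alike, collected over 90, 135 and 180 days.

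**Direction (hypothetical shares, not from the documents).** Take a low-dose group with share s on 60-day visits and the rest on 30-day visits. Its mean day for the fourth assessment is 90 + 90s: 112.5 for s = 0.25 and 135 for s = 0.5. A high-dose group is at day 105 if all attend weekly, or day 126 if all attend fortnightly. The gap, low minus high, is:

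- against weekly: 112.5 - 105 = +7.5 days to 135 - 105 = +30 days;
- against fortnightly: 112.5 - 126 = -13.5 days to 135 - 126 = +9 days.

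If PedsQL also rose by 0.2 to 0.5 SD per 90 days (again an assumption), the first case gives 7.5/90 × 0.2 = 0.02 SD to 30/90 × 0.5 = 0.17 SD. The second gives -13.5/90 × 0.5 = -0.08 SD to 9/90 × 0.5 = +0.05 SD. A fall in PedsQL reverses the signs, and a flat course gives zero. Neither sign nor size is fixed.

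**The case against.** The strongest reply is that few children are affected. Section IV.B.2 requires infusions roughly weekly for at least 3 months, and Section IV.B.3 repeats the roughly weekly schedule, so a child on 60-day visits from the start is an exception to the entry criteria. This stands as a limit on size. It does not remove the point, because Section IV.B.3 says that some children are not scheduled every 30 days and lengthens participation for them. Even exact weekly attendance puts the fourth assessment at day 105.

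A second reply is that the main analysis compares each child with itself, and the dose bands appear only in the power calculation. That is so. But the within-child 3-month estimate is the one that mixes follow-up times, and Section IV.B.3 says dose will enter the analysis in some form.

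A third is that the wording allows an approximate 3 months. That can cover day 105, but hardly day 180, which is twice as long.

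A reader might also infer that the late scores come from the children with the fewest sessions, so that the dose comparison is biased in a known direction. The documents do not support this. Under the assumed schedule a fortnightly attender has 7 sessions before day 90 (high band) and a fourth assessment on day 126, while a 30-day attender has 3 (low band) and a fourth assessment on day 90. Lateness does not rise steadily as dose falls.

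**Conclusion.** The point holds and should be fixed before dose is compared. As written, the plan lets one analysis occasion be day 90 for one child and up to day 180 for another, with no window, no maximum gap and no time term to separate them. It also gives no period for counting sessions. These gaps follow from the text; the particular days and session counts rest on regular visits and, for dose, one session per visit.

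The share of children affected is unknown, and so are the size and direction of any bias in the 3-month estimate or the dose comparison. The effect could be negligible if nearly all children attend weekly, and it is zero if PedsQL does not change over the days concerned. A claim of a specific inflated false-positive rate, or of a bias in one direction, would go beyond the documents.

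**What to change.** Add to Section IV.E:

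- **Model.** Analyze post-baseline PedsQL, and the secondary outcomes in the same way, with a linear mixed model: random intercept per child, actual days since baseline as the time variable, adjusted for the baseline score. Report the estimate at day 90 as the 3-month result. Fix the shape of the time trend in advance and check one alternative.
- **Dose.** Where dose enters, count the CAT sessions received before the assessment being modelled. Testing is at intake, so a session later that day is not counted. No session after an outcome is then used to explain it.
- **Sensitivity analysis.** Use the single assessment nearest day 90 within a stated window, for example days 70-110, with dose counted up to that assessment. In the schedules above this selects day 105 for weekly attenders (15 days from day 90, against 20 for day 70), day 84 for 14- and 21-day attenders, and day 90 for 30- and 45-day attenders. It drops 60-day attenders, which the report should say.
- **Reporting.** Show visit frequency alongside dose.

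The cost is one paragraph and a different model, with no added visits. The day-90 value for 60-day attenders is interpolated between days 60 and 120 and depends on the assumed time shape. Session dates must be recoverable from clinic records, since the plan names only number and type. For a child with regular visits, sessions accumulate in step with days, so the dose estimate rests largely on comparisons between children. Other differences between frequent and infrequent attenders remain.
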